5.3. Prior and Concomitant Medications

All prior medications, dictionary coded by WHO-DD, will be descriptively summarized for patients in the safety population. Summaries will present patient counts (and percentages) for all prior medications, by decreasing frequency of the overall incidence of ATC followed by therapeutic class. In case of equal frequency across anatomic or therapeutic categories, alphabetical order will be used. Patients will be counted once in each ATC category (anatomic or therapeutic) linked to the medication, but may be counted several times for the same medication.

All concomitant medications during the treatment period, dictionary coded by WHO-DD, will be descriptively summarized for patients in the safety population. Summaries will present patient counts (and percentages) for the concomitant medication groups described in Section 4.3 for all concomitant medications (including statin, non-statin LMT, CV), by decreasing frequency of the PRALUENT group incidence of ATC followed by therapeutic class. In case of equal frequency across anatomic or therapeutic categories, alphabetical order will be used. Patients will be counted once in each ATC category (anatomic or therapeutic) linked to the medication, hence may be counted several times for the same medication. Additionally, concomitant medications pre-specified as statin, non-statin LMT, and CV will be summarized by patient counts (and percentages) by therapeutic class or e-CRF pre-specified categories as appropriate and standardized medication name.

Post-treatment medications will be summarized as described above for all medications.

LMT (statins and other LMTs) use after enrollment will be summarized over time graphically BY? LMTs intensity at enrollment using the following categories:

- atorvastatin 40 to 80 mg daily or rosuvastatin 20 to 40 mg daily or;
- atorvastatin below 40 mg daily or rosuvastatin below 20 mg daily or simvastatin at any daily dose, or other statins
- LMT other than statin only,

July 16, 2020

• no LMT.

The LMTs intensity at baseline is defined as:

- patients treated at enrollment with atorvastatin 40 to 80 mg daily or rosuvastatin 20 to 40 mg daily (high intensity statin),
- patients treated at enrollment with atorvastatin below 40 mg daily or rosuvastatin below 20 mg daily or simvastatin at any daily dose (low intensity statin), or other statins;
- non-statin LMT only,
- no LMT.

5.4. Patient Disposition

Patient disposition includes the description of patient status at major milestone decisions in the study, as well as the patient analysis populations.

Patient study status will be summarized for the study. Summaries will provide the frequency (and percentage as applicable) of patients that met the criteria for the variables described in Section 4.4. Exception listings will be generated for any subject treated but not enrolled, enrolled but not treated.

Patient analysis populations will be summarized, depicting frequencies (and percentages) of patients that met the criteria for each population described in Section 3.

5.5. Extent of Study Treatment Exposure and Compliance

The extent of study treatment exposure and study compliance parameters for the treatment period described in Section 4.5 will be assessed and summarized for patients in the safety population.

5.5.1. Exposure to Investigational Product

Study treatment exposure for the treatment period will be descriptively summarized for the treatment duration and total number of injections as described in Section 4.5. Treatment duration will be summarized using the number of patients with data, mean, SD, median, minimum and maximum. Categorized 4-week intervals of treatment duration will be summarized descriptively by counts and percentages.

The incidence of premature study treatment discontinuation (irrespective of the reason) and premature treatment discontinuation due to AEs will be presented graphically in the safety population using the Kaplan-Meier method.

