# **10.6.** Statistical Considerations Surrounding the Premature Termination of a Study

If the study is terminated prematurely, only those parameters required for the development program and/or reporting to regulatory authorities will be summarized. Investigator and sponsor responsibilities surrounding the premature termination of a study are presented in Section 16.1.

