# 16. PREMATURE TERMINATION OF THE STUDY OR CLOSE-OUT OF A SITE

## **16.1. Premature Termination of the Study**

The sponsor has the right to terminate the study prematurely. Reasons may include efficacy, safety, or futility, among others. Should the sponsor decide to terminate the study, the investigator(s) will be notified in writing.

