1.1. Background/Rationale

This study is an open-label extension (OLE) to the neurocognitive function study (R727-CL-1532) in which all patients will be treated, in a single arm, with PRALUENT. The study will be conducted on patients who completed treatment and the end of study (EOS) visit in the neurocognitive function study (R727-CL-1532), with no premature discontinuation of study drug or placebo. This will allow for patient exposure to PRALUENT of approximately 6 years.

At the time of inclusion into the OLE study, knowledge of the treatment arm in the neurocognitive function study (R727-CL-1532) will not be available to the investigator or the sponsor. Patients eligible to participate in the OLE study will initiate treatment with PRALUENT at the starting dose of 75 mg once every 2 weeks (Q2W), regardless of the treatment group to which they were randomized in the neurocognitive function study (R727-CL-1532).

The study duration of approximately 192 weeks, in addition to the 96-week exposure in the neurocognitive function study (R727-CL-1532), will enable the assessment of long-term exposure to PRALUENT.

Following a Type II variation for Praluent submitted on 14 August 2019 to modify the EU RMP, the missing information "clinical impact of very low LDL-C for extended period of time" was removed from the RMP in the CHMP opinion dated Jan. 16,2020. The EMA agreed to release the R727-CL-1609 study as there is no expectation that this study can further characterize the safety profile of alirocumab beyond what has already been learned from other long-term, controlled studies. Therefore, the study was terminated early by sponsor on January 31, 2020. Given this early termination, all analyses will be considered descriptive.

PRALUENT is also referred to as alirocumab, REGN727 or SAR236553. In the context of the R727-CL-1609 SAP, it will be referred to as PRALUENT.

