1.2.2. Secondary and Exploratory Objectives

The secondary objectives of the study are:

- To describe the effect of PRALUENT on low-density lipoprotein cholesterol (LDL-C)
- To describe the effect of PRALUENT on other lipid parameters
- To describe the effect of PRALUENT on gonadal steroid hormones

1.2.3. Modifications from the Statistical Section of Protocol Amendment 2

Because this study was terminated early by the Sponsor, all analyses will be considered descriptive.

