4.4. Patient Disposition

Patient disposition includes the description of patient status at major milestone decisions in the study, as well as the patient analysis populations.

For patient study status, the following milestone categories are defined below. For all categories of patients, percentages will be calculated using the number of enrolled patients as the denominator, with two exceptions. Specifically, the two exceptions are for the screened and non-enrolled categories, which will not have associated percentages shown.

- Enrolled patients: met the inclusion criteria regarding the target indication and signed the informed consent form (ICF)
- Enrolled but not treated patients
- Enrolled and treated patients
- Patients complete 192 weeks of open-label treatment period (at least 190 weeks of exposure and visit W192 performed)
- Patients completed the study treatment period (i.e. as collected on the End of Open-Label Treatment eCRF)
- Patients who did not complete the study treatment period and patient's decision for treatment period discontinuation (as per the End of Open-Label Treatment eCRF)
- Patients who discontinued study treatment by main reason for permanent treatment discontinuation (as per the End of Open-label Treatment eCRF)
- Patients completed the study (i.e. as collected on the Study Completion eCRF)
- Patients who early terminated the study (as per the Study Completion eCRF)
- Patients who early terminated the study by main reason for early termination (as per the Study Completion eCRF)
- Status at last study contact
- Subject's visit impact due to COVID-19
- Study/Treatment discontinuation due to COVID-19

As defined in Section 3 of this document, the patient analysis populations are:

• Safety Population (SAF)

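### SAP 6.3 dates a missing last injection from a week-96 completer visit in a 192-week study; separately, SAP 5.5.1 gives its discontinuation curves no censoring rule

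*SAP*

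**What the plan says.** **Missing last-injection date.** For analysis periods and survival analysis, SAP 6.3 replaces an unknown last-injection date with the earliest of three candidates: the end of the known month (or year), the end-of-treatment visit, and the last contact. For completers it identifies the end-of-treatment visit as week 96. For patients who stopped early it uses their early end-of-treatment visit. Exposure duration and compliance are not imputed and stay missing.

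**Length of treatment.** SAP 2.1 plans about 192 weeks of open-label observation. SAP 4.4 has the row "Patients complete 192 weeks of open-label treatment period (at least 190 weeks of exposure and visit W192 performed". SAP 1.1 gives 96 weeks as the exposure in the parent study.

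**Cut-off tied to the last dose.** The by-visit summaries of laboratory values (SAP 5.7.2) and vital signs (SAP 5.7.3) use data up to 21 days after the last dose.

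**Discontinuation curves.** SAP 5.5.1 says: "The incidence of premature study treatment discontinuation (irrespective of the reason) and premature treatment discontinuation due to AEs will be presented graphically". It adds that the method is Kaplan-Meier in the safety population, and gives no censoring rule. SAP 1.1 records: "Therefore, the study was terminated early by sponsor on January 31, 2020". The consequence drawn in SAP 1.2.3 is: "Because this study was terminated early by the Sponsor, all analyses will be considered descriptive". Protocol 7.3.2.1 includes a request by the sponsor among the reasons for stopping study drug permanently.

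**The concern.** The week-96 visit in SAP 6.3 belongs to the parent study's length, not to this one. SAP 5.7 and 5.8 also describe time points as running from week 8 to week 96, although the window table in Appendix 10.1 runs to week 192, so text carried over from the parent plan is the likely source. Because the rule takes the earliest candidate, the week-96 visit wins even when the recorded month and year show a much later last injection. Later data from such a patient would then drop out of any summary whose cut-off depends on the last dose.

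The gap in SAP 5.5.1 matters because the study was closed by the sponsor while the 192-week plan was in force, and the SAP was written with that known. If patients whose treatment ended only because the study closed count as discontinuations, the any-reason curve falls on a timetable set by enrolment date. A reader would take it for persistence on drug.

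**Working it through.** **1. The plan's own study days.** Target day = 7 × week + 1. This reproduces all ten rows of the window table in Appendix 10.1, including week 96 = 7 × 96 + 1 = 673 and week 192 = 7 × 192 + 1 = 1345.

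**2. True last injection of a 192-week completer.**
- Minimum case: SAP 4.5 defines exposure in weeks as (last date + 14 − first date)/7. With 190 weeks, last − first = 190 × 7 − 14 = 1316 days, so the last injection is on day 1317.
- On-schedule case: with a last injection at week 190, the day is 190 × 7 + 1 = 1331.

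**3. Date under SAP 6.3 as written.** The week-96 visit, about day 673, is earlier than the true month end and the last contact, so it is chosen.
- 1317 − 673 = 644 days early.
- 1331 − 673 = 658 days (94 weeks) early.

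**4. Effect on the 21-day cut-off.** 673 + 21 = 694. The week-120 window opens on day 757, so nothing from week 120 onward is kept. Scheduled post-baseline visits, from protocol Table 1:

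| Assessment | Scheduled weeks | Lost | Kept |
|---|---|---|---|
| Hematology, chemistry | 24, 48, 72, 96, 120, 144, 168, 192 | 120, 144, 168, 192 (4 of 8) | 4 |
| Vital signs | 48, 96, 144, 192 | 144, 192 (2 of 4) | 2 |

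For the patient last injected on day 1331, the correct cut-off is 1331 + 21 = 1352, which includes the week-192 visit (day 1345), so the whole loss is due to the rule. For the minimum case it is 1317 + 21 = 1338, which already excludes a week-192 visit made within 3 days of target. The loss due to the rule is then 3 of 8 and 1 of 4.

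**5. What does not move.** SAP 4.7.1 ends the TEAE period at the last study visit, and PCSA counts use that period. Exposure and compliance stay missing. The rule also covers efficacy periods, but the SAP does not define where the on-treatment lipid period ends, so no lipid loss is counted here.

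**6. Discontinuation curves: mechanism only.** Let S(t) be the probability of not having stopped for other reasons by week t, and F the follow-up available when the study closed.
- Termination stops censored: cumulative discontinuation = 1 − S(t).
- Termination stops counted as events: 1 − S(t) × P(F > t).
- Difference: S(t) × [1 − P(F > t)], which is zero up to the shortest follow-up.

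Accrual and dropout are not in the documents. The following rests wholly on assumption: other stops at 4 to 8% per year (constant hazard, 52.18 weeks per year) and F uniform. At week 96, S = exp(−0.04 × 96/52.18) = 0.929 to exp(−0.08 × 96/52.18) = 0.863, so the censored curve reads 7.1 to 13.7%.

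| Assumed follow-up (weeks) | P(F > 96) | Difference at week 96 (points) |
|---|---|---|
| 98–150 | 1 | 0 |
| 52–156 | 60/104 = 0.577 | 36.5–39.3 |
| 60–130 | 34/70 = 0.486 | 44.4–47.8 |
| 26–130 | 34/104 = 0.327 | 58.1–62.5 |

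The spread follows the assumed accrual, so it shows the direction and is not an estimate for this trial.

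**The case against.** **On SAP 6.3.** The governing idea is the end-of-treatment visit, and the week-96 remark looks like a leftover that a programmer would probably notice. The rule applies only when the last-injection date is unknown. The study closed early, and no 192-week completer with a missing date is shown to exist. All of this stands, and it keeps the point minor. It does not make the text right, since the SAP is the specification and its literal result is wrong for the patients it describes.

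A reader might infer that the primary safety results are shortened, because SAP 4.6.1 words the endpoint as running to two weeks after the last dose. The planned analyses do not support that: the AE tables and PCSA counts use the TEAE period, which ends at the last study visit.

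**On SAP 5.5.1.** A reader might go further and say that the curves have no defined event, or that their clock could start at the parent study's first dose, because Appendix 10.1 mentions a double-blind dose. Neither holds. Both events are named. SAP 4.5 counts exposure from the first study treatment, the TEAE curves in SAP 5.7.1 start at the first dose, and the safety population is defined by dosing in this study. The appendix phrase concerns visit windows, and the note to its table counts from the first IMP injection. Nor does the lack of a termination row beside "Study/Treatment discontinuation due to COVID-19" in SAP 4.4 show much: that section tabulates main reasons from the eCRF and otherwise names none.

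It can also be said that the text already answers the question. The any-reason wording, together with the sponsor-request reason in protocol 7.3.2.1, points to counting termination as an event, and censoring would then be only a preferred display. Much of this stands, so the point is a request for clarification. Two things remain. SAP 4.4 also has "Patients completed the study treatment period (i.e. as collected on the End of Open-Label Treatment eCRF", and the documents do not show how that form records patients stopped by the closure. Protocol 10.6 limits what is summarized after early termination but gives no rule for these curves. Even on the literal reading, the later curve mixes persistence with enrolment timing.

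**Conclusion.** SAP 6.3 is wrong as written, at minor severity. The contradiction with the 192-week treatment period needs no assumption. For a 192-week completer with an unknown last-injection date, the error is 644 to 658 days, and visit summaries ending 21 days after the last dose lose up to 4 of 8 hematology and chemistry visits and up to 2 of 4 vital-sign visits. How many patients this touches is unknown and may be none.

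SAP 5.5.1 needs a clarification. It names its events but states no censoring rule and does not say how termination stops are handled. The literal reading counts them as events, and the any-reason curve beyond the shortest follow-up would then partly reflect when patients enrolled. The size cannot be determined from the documents. The effect is confined to a descriptive display: the two treatments agree up to the shortest follow-up, a closure of the study is not an AE discontinuation, and the by-reason tables and exposure categories remain.

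**What to change.** - **SAP 6.3:** replace the week-96 completer visit with the patient's actual end-of-treatment visit in this study (week 192 for 192-week completers).
- **SAP 5.5.1:** state that time runs from the first open-label injection. In the any-reason curve, count permanent discontinuations other than those caused by the study-wide termination, and censor termination stops and week-192 completers. State the censoring rule for the AE curve in the same place. Show numbers at risk under both curves.

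The cost is one corrected line, a few added sentences and a small programming change. No new data are needed if the End of Open-Label Treatment eCRF or the termination records identify patients stopped by the closure, which must be checked first.

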#### 7.3.2.1. Reasons for Permanent Discontinuation of Study Drug

Study drug dosing will be permanently stopped in the event of:

- Pregnancy, intention for pregnancy, or no longer using effective contraceptive method of birth control (females only). All pregnancies will be followed to their outcome.
- Acute injection reaction of clinical concern
- SAE (or non-serious but severe in intensity) of hypersensitivity reaction considered related to study drug
- At patient request, ie, withdrawal of the consent for treatment
- If, in the investigator's opinion, continued administration of study drug would be detrimental to the patient's safety or well-being. Any abnormal laboratory value will be immediately rechecked for confirmation before making a decision of permanent discontinuation of study drug
- At the specific request of the sponsor

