#### 8.1.1. Footnotes for the Schedule of Events Table

- 1. Patients who prematurely discontinue study treatment: any study treatment discontinuation should be initially considered temporary, and the investigator should make every effort to resume study drug treatment as early as possible, pending no safety concerns, and to perform all study visits and assessments as usual. When a treatment discontinuation is considered 'permanent', an extra visit (early termination visit) should be performed within 5 days of the decision to permanently discontinue study drug. This visit will be the last visit for the patient.
- 2. The end of study (EOS) visit of the double-blind neurocognitive function study (R727-CL-1532) corresponds to visit 1 (day 1) of the OLE study. Patients may enroll in the OLE study after completing treatment and the EOS visit in the neurocognitive function study (R727-CL-1532). The first SC injection of PRALUENT will be administered in the clinic (day 1, visit 1). After visit 1, patients have the option to either self-administer study drug, or have another designated person (such as a spouse or caregiver) administer study drug for them. Study drug should be administered Q2 weeks throughout the study.
- 3. The kit will include study drug and the study drug compliance log.
- 4. If at any time during the study after the week 8 visit, the investigator, based on lipid results or safety issue, decides to modify the dose of study drug, an unscheduled kit dispensation visit will be performed. During this visit, a call to the IVRS/IWRS will be performed.
- 5. Concomitant medication: received concomitantly to the study drug, from the time of informed consent to the final study visit.
- 6. Alcohol consumption within 48 hours and intense physical exercise within 24 hours prior to blood sampling for lipid parameters are discouraged.
- 7. Assessments completed at EOS in the neurocognitive function study (R727-CL-1532).
- 8. For male patients (luteinizing hormone [LH], follicle-stimulating hormone [FSH], and testosterone) and for female patients (LH, FSH, and estradiol). Menstrual cycle data will be collected for women of childbearing potential who are not on hormonal contraceptives.

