4.6.1. Primary Endpoint

The primary endpoint in the study is the incidence of AEs after first administration of study drug through the last dose of study drug plus 2 weeks.

The following AEs will be described:

- AEs/serious adverse events (SAEs)
- AEs leading to treatment discontinuation
- Adverse events of special interest (AESI)

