- All TEAEs regardless of relationship in one column and, in the same table a second column with TEAEs related to alirocumab according to investigator's opinion by primary SOC, HLGT, HLT and PT;
- All TEAEs by maximal severity (i.e., mild, moderate or severe), presented by primary SOC and PT, sorted as defined above;
- The event rate per patient-year (the number of patients with an event in question divided by total patient-years) will be provided for all TEAEs by SOC and PT. For a patient with event, patient year is censored at time of first event; for patient without event, it corresponds to length of TEAE period;
- Kaplan-Meier curves will be provided, when appropriate, for time from first dose of study treatment to the first occurrence of selected TEAEs as well as incidence

rates at 48, 96, 144, and 192 weeks of exposure. Patients without any event will be censored at the end of the TEAE period. Selected TEAEs could be AESIs (e.g neurocognitive events), or TEAE related to any clinically significant signal that needs further characterization;

The frequency of selected AEs by SOC and PT over time during the treatment period (number of patients experiencing AE and percentage by patient-months) will be provided, when appropriate, by time intervals defined as: ≤48 weeks, >48 to ≤96 weeks, >96 to ≤144 weeks, >144 to ≤192 weeks, using the PROC LIFETEST with the actuarial method. Only the first event will be counted.

Analysis of all treatment emergent serious adverse event(s)

- All serious TEAEs by primary SOC, HLGT, HLT, and PT and by SOC/PT; Patient listings of serious TEAEs will be provided for the report appendix.
- All serious TEAEs regardless of relationship in one column and in the same table a second column with TEAEs related to alirocumab according to investigator's opinion, by primary SOC, HLGT, HLT, and PT;
- The event rate per patient-year will be provided for all serious TEAEs by SOC and PT.

Analysis of all treatment-emergent adverse event(s) leading to treatment discontinuation

• All TEAEs leading to permanent treatment discontinuation, by primary SOC, HLGT, HLT, and PT and by SOC/PT; Patient listings of TEAEs leading to permanent treatment discontinuation will be provided for the report appendix.

Analysis of groupings of adverse events including selected adverse events of special interest

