5.7.1.1. Patient Deaths

The following summaries of deaths will be generated.

- Number (%) of patients who died by study period (TEAE and post-treatment);
- Deaths in enrolled but not treated patients;
- TEAEs leading to death (death as an outcome on the AE CRF page, as reported by the Investigator) by (at least) SOC (sorted by internationally agreed order), and PT (sorted by decreasing frequency, showing the number (n) and percentage (%) of patients) for the safety population.

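### The Kaplan-Meier curve for discontinuation due to AEs (SAP 5.5.1) slightly overstates the incidence it is meant to show, because other permanent stops and some deaths can enter it only as censored

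*SAP*

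**What the plan says.** SAP 5.5.1 describes two curves in one sentence. The first is "The incidence of premature study treatment discontinuation (irrespective of the reason"), the second the AE-specific one: "premature treatment discontinuation due to AEs will be presented graphically in the safety population using the Kaplan-Meier method". Both are described as incidence. The section defines neither the event nor the censoring for the AE curve, and neither document mentions competing risks or a cumulative incidence function.

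The nearest written rule is in SAP 5.7.1, for Kaplan-Meier curves of selected TEAEs: "Patients without any event will be censored at the end of the TEAE period". SAP 5.8 has a similar rule for the LDL-C events.

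Other permanent stops are foreseen. Protocol 7.3.2.1 lists, among others, "At patient request, ie, withdrawal of the consent for treatment", pregnancy and a sponsor request. After a permanent stop there is one early termination visit, and Protocol 8.1.1 (footnote 1) says: "This visit will be the last visit for the patient". Deaths are expected and tabulated in SAP 5.7.1.1 ("Number (%) of patients who died by study period (TEAE and post-treatment")). The reason for stopping is recorded, since SAP 4.4 reports "Patients who discontinued study treatment by main reason for permanent treatment discontinuation".

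SAP 4.6.1 names "AEs leading to treatment discontinuation" among the three groups of events described under the primary endpoint.

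**The concern.** A patient who has permanently stopped for another reason has left treatment and, after one visit, the study. That patient cannot later stop for an AE. The stop is a competing event, not incomplete follow-up. Censoring it makes one minus Kaplan-Meier (1-KM) estimate the risk in a setting where nobody stops for any other reason, and only if such stops are independent of AE stops. The SAP asks for the incidence, which is a different quantity.

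Two things follow. The curve cannot lie below the true cumulative incidence, and it lies above it once AE stops occur after other stops. Also, cause-specific 1-KM curves sum to more than the all-reason curve, so the two curves planned in the same sentence cannot be read together as parts of a whole.

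**Working it through.** **Inputs from the documents.** About 1,600 patients expected (Protocol 6.1). Planned treatment about 192 weeks (SAP 2.1), which is 192/52.18 = 3.68 years. Study ended by the sponsor on 31 January 2020 (SAP 1.1). Enrolment dates and rates of AE stops, other stops and death are not given, so there is no figure of the plan's own to reproduce.

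**Assumptions.** Constant hazards: a = 1-3% per year for AE stops, o = 3-10% per year for other stops including competing deaths; middle case a = 2%, o = 6%.

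**Formulas**, for follow-up of T years:
- 1-KM with other stops censored: 1 - exp(-aT)
- Cumulative incidence (CIF): a/(a+o) × [1 - exp(-(a+o)T)]
- Greenwood SE of the Kaplan-Meier estimate, if all are followed to T: exp(-aT) × sqrt{ a/[n(a+o)] × [exp((a+o)T) - 1] }

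**Middle case, every patient followed 144 weeks** (T = 144/52.18 = 2.76):
- 1-KM = 1 - exp(-0.0552) = 5.37%
- CIF = 0.25 × [1 - exp(-0.2208)] = 0.25 × 19.81% = 4.95%
- Excess = 0.42 points
- SE = 0.946 × sqrt(0.25 × 0.247/1600) = 0.59 points, so the excess is 0.71 SE

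**Across the assumed rates:**

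| Follow-up | Middle case, 1-KM vs CIF | Middle excess | Range of excess |
|---|---|---|---|
| Uniform over 96-144 weeks, read at 120 weeks | 4.50% vs 4.20% | 0.29 points, 0.53 SE | 0.08-0.70 points, 0.19-1.02 SE |
| 144 weeks for all | 5.37% vs 4.95% | 0.42 points, 0.71 SE | 0.11-0.99 points, 0.26-1.36 SE |
| Full 192 weeks for all | 7.09% vs 6.37% | 0.72 points, 1.06 SE | 0.19-1.68 points, 0.40-1.99 SE |

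In the first row the SE also allows for the patients censored between 96 and 120 weeks. Read close to the end of that follow-up, few patients remain at risk and the SE grows, so the ratio falls to about 0.43 SE in the middle case and about 0.16 SE at the lowest rates.

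**Additivity, middle case at 144 weeks.** The all-reason curve is 1 - exp(-0.2208) = 19.81%. The two 1-KM figures are 5.37% and 1 - exp(-0.1656) = 15.26%, which sum to 20.63%. The two CIFs are 4.95% and 0.75 × 19.81% = 14.86%, which sum to 19.81%.

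**Simulation check.** With 1,600 patients per trial, full 192-week follow-up, a = 2% and o = 10% per year, mean 1-KM was 7.14%, mean CIF 5.99%, and the share who actually stopped for an AE 5.99%. With o = 0 the two formulas agree, so administrative censoring alone produces no gap.

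**The case against.** The strongest reply is that little depends on this graph. A reader might infer that a primary-endpoint result is biased. The documents do not support that. AEs leading to permanent discontinuation are reported as n (%) in the TEAE overview and by SOC, HLGT, HLT and PT, with the safety population as denominator (SAP 5.7.1), and disposition counts stops by main reason (SAP 4.4). None of these uses Kaplan-Meier. All analyses are descriptive after the early termination (SAP 1.1, 1.2.3). This stands and keeps the point small.

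The size rests on assumed rates and an expected sample size. This also stands. The ratio to the SE scales with the square root of n: at an illustrative 800 patients the 144-week middle case falls from 0.71 to 0.71/√2 = 0.50 SE. At 3% per year of other stops, every early-termination case is below half an SE. The direction does not depend on the rates.

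A reader might expect a cumulative incidence curve to match the crude tables. It will not when follow-up is unequal. With follow-up spread over 96-144 weeks, the middle-case CIF near the end is about 4.95% against a crude 4.20%, a gap of 0.75 points, larger than the correction of about 0.4 points. The case for the change is the meaning of the curve and its additivity, not agreement with the tables.

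Finally, the censoring is inferred from the method. It would go too far to say that the SAP censors all deaths: a fatal AE may be recorded as an AE discontinuation and counted as an event. Only deaths not so classed are in question.

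**Conclusion.** The point holds for one descriptive graph that supports a named safety component. As planned, the curve overstates the incidence of discontinuation due to AEs and does not fit together with the all-reason curve. Under the assumed rates and n = 1,600, the excess with early termination is about 0.1 to 1.0 points (about 0.15 to 1.4 SE), with a middle case of about 0.3 to 0.4 points (0.5 to 0.7 SE). The range of 0.2 to 1.7 points needs the full 192 weeks, which the termination cuts short for some or all patients, so it should not be taken as the expected size.

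Two wider readings are not supported. The study-wide termination is not itself a competing event: patients still on treatment then are properly censored. Nor do the AESI curves need the same change on account of death. With assumed AESI rates of 0.5-2% and death rates of 1-2% per year, the shift there is only 0.10 to 0.39 SE.

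**What to change.** In SAP 5.5.1:

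- Keep Kaplan-Meier for discontinuation irrespective of reason, and state that death counts as a stop.
- For discontinuation due to AEs, present the Aalen-Johansen cumulative incidence function (PROC LIFETEST with EVENTCODE= in SAS 9.4, the version already named in SAP 8).
- Define the event. Name as competing events patient-level stops for any other reason and deaths not classed as AE discontinuations.
- Censor patients who complete the planned treatment at completion, and patients still on treatment at the study-wide sponsor termination at that date.
- SAP 4.4 lists no reason categories. If the eCRF reason does not separate study-wide termination from a sponsor request for one patient, use the stop date relative to 31 January 2020 to separate them.

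The cost is SAP wording, one procedure option and this classification step. The AE curve becomes slightly lower; the crude tables do not change.
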